10.2.2.2 Participants for sensitivity analyses, per type of SLE SOC (biologics and nonbiologics)

For the primary outcomes (objectives 1 to 4), sensitivity analyses will be performed to compare patients exposed to anifrolumab with two groups of patients exposed to SLE SOC: patients exposed to SLE SOC biologics and patients exposed to SLE SOC non-biologics. Additional sub-cohorts will be re-assessed from the *overall source population* (obtained in step 1, Section 10.2.2.1). Patients initiating anifrolumab will be matched with comparable patients not exposed to anifrolumab but exposed to SLE SOC biologic drugs (belimumab or rituximab, including biosimilars) and with those exposed to SLE SOC non-biologics.

Subgroup cohorts (for malignancy and serious infection outcomes) (Table 5) will consider the same inclusion and exclusion criteria described for the main analyses (Section 10.2.2.1) from step

2 until step 4. However, at step 2 (for exposed to anifrolumab) and at step 4 (for unexposed to anifrolumab) the following additional criteria will be applied:

- Exposed patients: exclusion of patients with a prescription of SLE SOC biologics (belimumab or rituximab) in the previous 12 months.
- Unexposed to anifolumab patients, exposed to SLE SOC biologics: inclusion of patients with a prescription of SLE SOC biologics in the previous 12 months regardless of other SLE SOC).
- Unexposed to anifolumab patients, exposed to SLE SOC non-biologics: inclusion of patients with a prescription of SLE SOC and exclusion of those with a prescription of SLE SOC biologics in the previous 12 months.

			Additional criteria to	
	Input	Exposed and unexposed	be applied at STEP 2	Sub-cohorts created at
Outcome	population	units	to the input	STEP 4
			population	
Malignancies	Overall	Exposed to anifrolumab	EXCLUSION:	malign_sub_exp
	source		Patients exposed to SLE	
	population		SOC biologics in the	
		I I a serve a set da ser i fa share sh	previous 12 months	
		Unexposed to anifrolumab	INCLUSION: Patients with SLE SOC	malign_sub_unexp_bio
		(exposed to SLE SOC		
		biologics)	including a biologic	
			drug in the previous 12	
			months	
		Unexposed to anifrolumab	EXCLUSION:	malign_sub_unexp_nonbio
		exposed to SLE SOC non-	Patients exposed to SLE	
		biologics	SOC biologics in the	
			previous 12 months	
Serious	Overall	Exposed to anifrolumab	EXCLUSION:	inf_sub_exp
Infections	source		Patients exposed to SLE	
	population		SOC biologics in the	
			previous 12 months	
		Unexposed to anifrolumab	INCLUSION:	inf_sub_unexp_bio
		(exposed to SLE SOC	Patients with SLE SOC	
		biologics)	including a biologic	
			drug in the previous 12	
			months	
		Unexposed to anifrolumab	EXCLUSION:	inf_sub_unexp_nonbio
		exposed to SLE SOC non-	Patients exposed to SLE	
		biologics	SOC biologics in the	
			previous 12 months	

Table 5 Subgroup cohorts for sensitivity analyses by SLE SOC treatment

Abbreviations: SLE: systemic lupus erythematous; SOC: standard of care.

10.3 Variables

Variables used in this study are divided into exposure of interest (Section 10.3.1), outcome parameters of interest (Section 10.3.2), and participants characteristics and potential confounding variables (Section 10.3.3). The availability and contents of different specific variables is expected to vary between data sources. Accordingly, the inclusion, selection, and definition of specific variables may vary across data sources. Specific variable definitions will be detailed and provided as part of local protocols and the statistical analysis plan (SAP).

In this protocol, the 2019 WHO International Statistical Classification of Diseases and Related Health Problems, 10th Revision (ICD-10) has been used as the coding system for definition of diagnoses, and procedures [98].

International non-proprietary names are used as nomenclature for prescription drugs. World Health Organisation (WHO) Anatomical Therapeutic Chemical (ATC) classification system will be used for all prescription drugs in this protocol.

The ICD-10 and ATC codes used in this protocol for variable definitions will be amended to the relevant coding systems, as appropriate for the respective data sources, and will be provided in the SAP.

10.3.1 Exposure definition and variables

Exposure to the study drugs will be ascertained from recordings of outpatient visits, procedures, prescriptions dispensed at community pharmacies, and insurance claims registrations as available in the different data sources. Data availability regarding unit dose, frequency of administration, duration of therapy (start and stop dates), and dose adjustments was part of the feasibility assessment and detailed in Section 10.4.

10.3.1.1 Study drugs

SLE standard treatments can include a variety of drugs used alone or in combination, including antimalarials, glucocorticoids, immunosuppressants (synthetic and biologics), immunoglobulins and plasmapheresis (Table 14).

10.3.1.1.1 EXPOSED GROUP (ANIFROLUMAB)

The exposure of interest is anifrolumab (brand name SAPHNELO). According to the drug indication, anifrolumab is expected to be prescribed as an add-on therapy to SLE SOC. Due to the long study duration, the therapeutic indication for anifrolumab and method of administration may change over time. This may result in future use of anifrolumab without SOC indicated for moderate to severe SLE or in other forms of anifrolumab administration (e.g., subcutaneous administration). Therefore, to capture all patients exposed to anifrolumab, no requirement for concomitant SLE SOC use will be applied. Anifrolumab will be identified using the ATC code L04AA51 (or the appropriate country-specific coding system), irrespective of the administration route.

10.3.1.1.2 STANDARD OF CARE FOR MODERATE TO SEVERE SLE

In current study, SOC indicated for moderate and severe SLE, is defined as the use of any one of the following (either in addition to antimalarials and/or low dose corticosteroids or not) [33, 42, 58]:

- Medium or high dose corticosteroids (prednisolone equivalent dose ≥7.5 mg/day) either through oral or intravenous (IV) routes; or
- Immunosuppressants:
 - synthetic (e.g., azathioprine, methotrexate) or specific (e.g., janus kinase inhibitors such as tofacitinib); **or**
 - biologics (e.g., belimumab, rituximab): **or**
- Plasmapheresis; or
- IV immunoglobulins.

The selection of drugs included in the code list for SOC indicated for moderate and severe SLE is detailed in Table 14. It includes all drugs that moderate and severe SLE patients could be exposed to (including antimalarials), based on 2019 EULAR guidelines [33], published literature [49, 50, 60, 64, 75] and inputs from medical advisors. Drugs that are not in any of the provided references, or that failed in SLE clinical trials have not been included. Furthermore, the list does not consider emerging therapeutic agents (in Phase 2/3 development), as the efficacy of these therapeutic agents in the management of SLE have not been established.

Additional drugs with indication for moderate to severe SLE that are launched in any of the study countries during the study period may be considered as part of SLE SOC. Any changes in the SLE SOC code list will be communicated to PRAC in the interim reports.

10.3.1.2 Exposure assessment

Exposure will be classified using an on-treatment approach, i.e., patients will be considered exposed until the end of treatment episode or censoring. Specific criteria for malignancies and infections cohorts are detailed in Section 10.3.1.2.1 and Section 10.3.1.2.2, respectively.

Treatment episodes for patients exposed to anifrolumab

The first anifrolumab treatment episode will be considered⁴. The treatment episode is the continuous time from the date of the first prescription or administration (depending on the available data) until discontinuation plus the window of clearance (Figure 5).

Discontinuation date will be calculated from the treatment start date plus the days covered by therapy if no subsequent prescription is registered after that period. **Days covered by therapy** will be based on the recommended dosing frequency for anifrolumab, i.e., it will be 30 days (4 weeks). For patients exposed to anifrolumab, duration of treatment episode will be defined regardless of concomitant use of SLE SOC.

The **window of clearance** will be defined as the time for concentration to fall below the lowest level of quantification (LLoQ) for 95% of patients. The anifrolumab window of clearance will be defined as 16 weeks.

[figure not shown]

Figure 5 Treatment episodes definition for patients exposed to anifrolumab * No concomitant SLE SOC was presented for simplicity.

Abbreviations: SLE, systemic lupus erythematosus; SOC, standard of care

⁴Only first treatment is included because after anifrolumab discontinuation patients using SLE SOC may not be comparable with the non-anifrolumab users. Anifrolumab will be used as maintenance therapy and previous Randomised Controlled Trials' (RCT) results [7, 92] showed low frequency of discontinuation (until 3 years of treatment). The main reasons for anifrolumab discontinuation are expected to be adverse events (such as allergic reactions and infections) and lack of effectiveness of the drug [7], which are not likely to result in anifrolumab re-initiation. Thus, the number of anifrolumab re-starters is expected to be low and patients are likely to be different from first users. Additionally, it is not known if the risk of adverse events returns to baseline after anifrolumab discontinuation and how different are patients' characteristics after anifrolumab discontinuation.

Treatment episodes for patients unexposed to anifrolumab – exposed to SLE SOC

The **first treatment episode** is the continuous time from the date of first prescription of a SLE SOC treatment after diagnosis of moderate to severe SLE until the first date of discontinuation of that treatment plus the window of clearance (Figure 6). The index date will be assigned as the date of prescription within the time interval of the anifrolumab index date for the corresponding exposed patient (Section 10.2.2.1). Different SLE SOC drugs used (as add-on or switching between drugs) will not be counted as a different treatment if prescribed before the end of the window of clearance (patients 2 and 3 in Figure 6).

Discontinuation date will be calculated from the treatment start date plus the days covered by therapy if no subsequent prescription is registered after that period. **Days covered by therapy** are specific for each drug and will be estimated by the expected supply duration. For biologics, the period covered by a prescription will be based on the recommended dosing frequency for each biologic.

The **window of clearance** is specific for each drug and will be defined as five times the terminal half-life of the SLE SOC, or the time for concentration to fall below the lowest level of quantification (LLoQ) for 95% of patients where applicable.

After that period, if no SLE SOC prescriptions are registered, patient will be censored. Additionally, start of anifrolumab will dictate the end of SLE SOC treatment episode (patient 4, Figure 6). At the time of anifrolumab initiation patients will be considered as part of the group of patients exposed to anifrolumab.

[figure not shown]

Figure 6 Treatment episodes definition for patients unexposed to anifrolumab (SLE SOC) Abbreviations: SLE, systemic lupus erythematosus; SOC, standard of care

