STEP 3 – **Identification of patients exposed to anifrolumab for the outcome-specific source** population

At step 3, the malignancy and serious infection source populations will be created.

Step 3a. Exposed patients in the malignancy source population

Additional exclusion criteria to be applied to the exposed patients:

• A diagnosis of any malignancy prior to index date.

³ According to the SLE severity algorithm, most moderate to severe patients will be those with a previous exposure to SOC indicated for moderate to severe disease. A very small group of patients, defined as having moderate/severe SLE based on the existence of SLE-related comorbidities, will not have a prescription of SOC for moderate/severe SLE.

Step 3b. Exposed patients in the serious infection source population

Additional exclusion criteria to be applied to the exposed patients:

- A diagnosis of any malignancy prior to index date.
- A diagnosis of HIV/AIDS or congenital immunodeficiency prior to index date.
- Organ or bone marrow transplant procedure prior to index date.
- A diagnosis of serious infection in the previous 6 months.

STEP 4 – **Time-based exposure sets**

This step is defined to create the time-based exposure sets, from the outcome-specific source populations. For each patient exposed to anifrolumab (identified in steps 3a and 3b) all unexposed patients from the source population (step 2b) that meet the following criteria will be included as unexposed patients.

Step 4a. Malignancy time-based exposure set

Patients exposed to anifrolumab from the malignancy source population (step 3a) and patients unexposed to anifrolumab (step 2b). Inclusion criteria for patients unexposed to anifrolumab (exposed to SLE SOC):

- At least a prescription of SOC indicated for moderate to severe SLE (Table 14).
- Duration of the previous exposure to SLE SOC similar to the SLE SOC duration of the corresponding exposed patient (+/- 45 days [wider time intervals may be considered if matches cannot be obtained using this time window]), at index date. The **index date** for the patient unexposed to anifrolumab will be the SLE SOC prescription date that will result in length of the SLE SOC treatment closer to SLE SOC treatment of the corresponding exposed patient.
- No prescription for anifrolumab prior to index date.
- A minimum data availability of 12 months prior to index date.
- Age ≥ 18 years at index date.

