10.3.1.2.2 FOLLOW-UP FOR THE SERIOUS INFECTION COHORT

For the serious infection primary and secondary objectives, follow-up starts at index date and ends at the end of the treatment episode (Figure 8), occurrence of a serious infection or at any of the **censoring** events (loss to follow-up for disenrollment/de-registering, death, or end of the study period/date of data extraction), whichever occurs first.

For the exploratory objective, follow-up ends at the end of treatment episode or any of the censoring events: loss to follow-up for disenrollment/de-registering, death, or end of the study period/date of data extraction, whichever occurs first.

Figure 8 Follow-up assessment for the serious infection cohort (main analysis) Abbreviations: SLE, systemic lupus erythematosus; SOC, standard of care

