10.7.1 Statistical methods

10.7.1.1 Time-based exposure sets and propensity score matching

Base cohort

The base cohort will be defined using SLE diagnosis within the study period as the inclusion criteria. Anifrolumab exposed patients in the base cohort will consist of individuals who had prior exposure to SLE SOC drugs. Hence, the base cohort will be formed of all patients who have used SLE SOC, some adding-on anifrolumab as incident user, and the others continuing SLE SOC alone.

Time-based exposure sets

Time-based exposure sets will be defined to determine the time-points at which comparability will be established. Time on SLE SOC (i.e., time from the first prescription of SLE SOC for moderate to severe SLE) will be considered as a marker of disease course. For each exposed patient, a time-

based exposure set will be created including all unexposed patients with similar time on SOC as the exposed at the time of anifrolumab initiation. Anifrolumab and SLE SOC prescriptions dates will be used to anchor the exposure sets from the base cohort [88]. The detailed process of time-based exposure set creation is presented in Section 10.1 and in Section 10.2.2.1.

Time-conditional propensity score-based matching

Time-conditional propensity scores will be used to compute, for each patient in each time-based exposure set, the propensity of being exposed to anifrolumab (vs. staying on SLE SOC) as a function of patient characteristics at the exposure risk set date. Variables identified as potential confounders included in Table 6 will be considered for inclusion in the time-conditional propensity score. The steps involved in creation of time-based exposure sets and PS matching are below:

- 1. In the base cohort, each patient is treated as a possible comparator in the beginning until exposure of anifrolumab or censoring due to other reasons.
- 2. The index date for patients in the exposed group is their anifrolumab first exposure date.
- 3. On a timescale of time since start of SLE SOC, for each timepoint where a patient is exposed to anifrolumab, the set of eligible comparators is formed based on time since the start of SLE SOC.

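### The comparator's treatment episode is tied to the first SOC prescription instead of the index prescription, so a comparator with a full SOC gap before index has no valid follow-up

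*Protocol*

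**What the plan says.** **Comparator episode (section 10.3.1.2).** A single episode is defined, as "the continuous time from the date of first prescription of a SLE SOC treatment after diagnosis of moderate to severe SLE". The same sentence then fixes where it stops: it runs "until the first date of discontinuation of that treatment plus the window of clearance". An added or switched drug "will not be counted as a different treatment if prescribed before the end of the window of clearance".

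**Comparator index date (section 10.2.2.1, step 4).** The index date "will be the SLE SOC prescription date that will result in length of the SLE SOC treatment closer to SLE SOC treatment" in the matched anifrolumab patient. Section 10.7.1.1 measures time on SOC as "time from the first prescription of SLE SOC for moderate to severe SLE". Its step 4 asks only for an SOC prescription within 45 days either side on that scale, with the option of a wider interval. Neither section requires SOC use to have been continuous up to index.

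**Follow-up.** For serious infections, "follow-up starts at index date and ends at the end of the treatment episode" (section 10.3.1.2.2), unless an event or censoring comes first. For malignancies, it starts 12 months after index and ends at the latest 12 months after the end of the treatment episode (section 10.3.1.2.1).

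**Exposed arm (section 10.3.1.2).** The anifrolumab episode starts at the first anifrolumab prescription, which is the index date. Its length does not depend on SOC use.

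**The concern.** The start of follow-up and its end come from two different anchors in the comparator arm. The start is the index prescription, which can lie well after SOC began. The end belongs to the episode that opened with the first SOC prescription. If that episode closed before index, there is no time at risk.

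Three things are at stake for the primary comparisons (objectives 2 and 4):

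- **One-sided selection.** Comparators contribute time only if SOC was not fully interrupted beyond clearance up to index. Exposed patients face no such condition. The design is meant to make SOC history comparable between arms.
- **Wasted matches.** Matching may select such a comparator, who is then removed from all later exposure sets (section 10.7.1.1, step 9). Balance is checked on the matched set (step 10), which would differ from the set that contributes person-time.
- **Uneven repair.** German and Spanish data are analysed by the data providers (section 10.6). Programmers who meet negative follow-up could resolve it differently before the results are pooled.

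**Working it through.** There is no stated figure to reproduce, because the point concerns a definition. The check is date arithmetic on the protocol's own rules.

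**Notation.** Days are counted from the first SOC prescription. *I* is the comparator's index date. *C* is the last day covered before the gap. *w* is the clearance window. *E* = *C* + *w* is the end of the first episode, when no SOC is prescribed by then.

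**Maximum follow-up under the written rule**

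- Serious infections: *E* - *I*.
- Malignancies: (*E* + 12 months) - (*I* + 12 months) = *E* - *I*.

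The 12-month latency and the 12-month extension cancel, so both cohorts fail under the same condition, *E* at or before *I*.

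**Example.** Section 10.7.1.1, step 4a, has an exposed patient starting anifrolumab at day 180; comparators need an SOC prescription between day 135 and day 225. Take a comparator covered to day 60 who restarts SOC on day 170. This patient is eligible, with *I* = 170. The coverage dates and the values of *w* are assumptions; the protocol makes *w* drug-specific.

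| *w* (days) | *E* = 60 + *w* | Serious infection: *E* - 170 | Malignancy start: 170 + 365 | Malignancy end: *E* + 365 | Malignancy follow-up |
|---|---|---|---|---|---|
| 7 | 67 | -103 | 535 | 432 | -103 |
| 28 | 88 | -82 | 535 | 453 | -82 |
| 56 | 116 | -54 | 535 | 481 | -54 |
| 112 | 172 | episode continues | 535 | – | valid |

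In the last row the restart on day 170 falls before day 172, so the gap is bridged. In the malignancy cohort the nominal end falls after index, but still before that cohort's own start of follow-up.

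**The same history in the exposed arm.** An anifrolumab initiator with the same SOC gap has an episode that opens at index, so follow-up is positive.

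**After the correction.** If the episode is the one that contains the index prescription, *E* cannot precede *I* for any eligible comparator.

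**Scale of lost comparators.** The sample sizes assume 1:3 matching. Losing two of every three comparators would move the study from the 1:3 to the 1:1 power tables (HR 1.5, SD 0.2). For malignancies at 3,500 exposed and 6.31 per 1000 person-years, power falls from 0.814 to 0.663 (Tables 10 and 9). For serious infections at 1,500 exposed and 39.8 per 1000 person-years, it falls from 0.835 to 0.710 (Tables 12 and 11). This shows what a loss of that size would cost; nothing in the protocol says it would be that large.

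**The case against.** **The text can be read more kindly.** Discontinuation is declared only when no later prescription is registered, and every comparator has one at index. The Abstract attaches *first* to anifrolumab only and refers simply to the SOC treatment for comparators. Figure 6, which shows worked patients, is not reproduced in the text at hand. This supports the view that the intended episode was the one running at index. It does not rescue the wording. If any later prescription cancelled a discontinuation, years off drug would count as exposed, and both the reference to a *first* discontinuation and the clearance limit on switches would have no function. The footnote in the same section also treats restarting anifrolumab after discontinuation as a separate matter, so a later prescription does not undo a discontinuation.

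**The gap must be a full one.** This stands. Switches and add-ons within clearance do not end the episode; only a gap in all SOC beyond days covered plus clearance does. The anchor is also the first prescription after diagnosis of moderate to severe SLE, not necessarily the first in a lifetime.

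**Few patients may be affected.** Section 10.9 expects few patients to be off all SOC, and comparators need a flare in the six months before index. That bears on size, and no figure is given. Assumed full-gap rates of 0.05 to 0.5 per year, through exp(-rate × years), leave 95% to 61% gap-free after one year and 78% to 8% after five. A range that wide settles nothing, so a reader should not infer that a large share is lost.

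**The direction of bias is open.** A reader might infer that persistent SOC users are lower-risk survivors and that the hazard ratios are therefore too high. The document does not establish this. Serious infection in the previous six months is an exclusion in both arms of that cohort, while earlier infections and prior SOC are candidates for the propensity score. Longer unbroken immunosuppression could also raise comparator risk and push the ratio down.

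**The SAP could settle it.** Detail can be left to the SAP, but here the protocol states a rule. An SAP that got it right would have to contradict section 10.3.1.2.

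**Conclusion.** The definition is wrong as written. Section 10.3.1.2 conflicts with the index-date and eligibility rules in sections 10.2.2.1 and 10.7.1.1. Every matched comparator whose full SOC gap outlasted clearance before index has no valid person-time in either cohort, while exposed patients with the same history are retained. This follows from the text and needs no assumption about gap rates.

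A reader might go on to say that only never-interrupted SOC users remain. The protocol states no such exclusion: these patients can be matched and then contribute nothing, and shorter interruptions are harmless. The number affected and the direction of any bias remain unknown. The point still needs correcting before programming, because the rule governs person-time for both primary outcomes and affects one arm only.

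**What to change.** In section 10.3.1.2, replace the comparator definition with wording such as: *For each matched comparator, the treatment episode is the continuous SOC episode that contains the index prescription. Time at risk is counted from the index date to the first discontinuation after the index date plus the clearance window, or to the start of anifrolumab if earlier.* The malignancy cohort keeps its 12-month latency and its 12-month extension. Time since first SOC prescription stays as the matching time scale only, computed the same way in both arms. Figure 6 should be checked against the new wording.

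The cost is one sentence in the protocol and the matching line in the programming specification. It needs no further data or patients, and no eligible comparator is lost to negative follow-up.
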